## 11.0 Data Management

- The primary outcome of interest is the inspiratory capacity obtained in the PACU via the incentive spirometer.
- The secondary outcomes that will be observed are the numerical value for SPO2, SPO2 trend, and use or lack thereof of supplemental O2 in PACU in 15 minute intervals or up to two hours after arrival there.

- Our primary hypothesis is that subjects that will have lung protective strategies employed on them will have 20% superior mean inspiratory capacity breaths via incentive spirometry compared to the non-intervention controls.
- Only IRB approved study team members will have access to data. Each study subject will be given a study ID number that will be used to identify them throughout the study. All study staff will have their CITI certification and receive protocol training. All data will be kept on a password protected MUSC server and in a redcap database. All paper documents will be kept in a locked office, in a locked cabinet that only IRB study team members have access to.
- Our primary hypothesis is that use of lung protection protocol will result in smaller change in lung function, measured by Incentive Spirometry (IS).

$H_0$ : change in ISI ≠ change in ISC

$H_A$ : change in ISI < change in ISC

The primary analysis will be a two-sided test of mean change in IS after surgery compared to pre-surgery IS.

Based on data from a study of 19 people undergoing lobectomy {Bastin, 1997 #14268}, we assume that the IS before surgery is 2642 mL (se=140; std=610). If the control group IS decreases by 40%, the mean change in the control group will be ~1000 mL (std dev=308). Assuming the intervention group IS decreases by 30%, the mean change in the intervention group will be ~800 mL. Assume shared std dev=350.

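### The effect size of 0.667 used for the sample size does not follow from the stated mean changes and SD of 350 mL, so the stated 37 per group, 80% and 91% power are unsupported

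*Combined protocol and SAP*

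**What the plan says.** All of the sizing is in section 11.0 Data Management. Pre-operative incentive spirometry (IS) capacity is taken as 2642 mL. For a 40% fall in controls, "the mean change in the control group will be ~1000 mL (std dev=308"). For the other arm: "Assuming the intervention group IS decreases by 30%, the mean change in the intervention group will be ~800 mL". A shared SD of 350 mL is then assumed.

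The two G*Power runs in the same section are two-tailed at alpha 0.05 and both enter d = 0.6666667. The first returns 37 per group for 80% power. The second returns 91% power at 50 per group. The text presents the step from 37 to 50 as cover for withdrawals and gives no withdrawal rate.

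On the hypothesis, section 11.0 makes two statements, each labelled primary. One is that intervention subjects "will have 20% superior mean inspiratory capacity breaths via incentive spirometry compared to the non-intervention controls". The other is that "use of lung protection protocol will result in smaller change in lung function". The formal alternative is "change in IS I < change in IS C" and the null is printed as "change in IS I ≠ change in IS C". The analysis is then specified: "The primary analysis will be a two-sided test of mean change in IS after surgery compared to pre-surgery IS". Section 6.0 Number of Subjects describes the target as a 20% difference in the anticipated decrease.

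**The concern.** The effect size is the only link between the clinical assumptions and the sample size. If it does not come from the stated difference and SD, the stated n and power are correct for an effect that the plan never describes. What is at stake is whether the 13 subjects per group between 37 and 50 are a real attrition allowance. This matters because section 14.0 Withdrawal of Subjects provides for withdrawal on several grounds, including post-operative ventilation, ICU admission and unmet ventilation goals.

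The hypothesis wording adds to the difficulty: the 20% is attached to capacity in one place and to the decrease in another, and these are effects of different size.

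**Working it through.** **Inputs (section 11.0).** Baseline 2642 mL; losses 40% and 30%, rounded to about 1000 and 800 mL; SD 350 mL shared and 308 mL for the control change; two-sided alpha 0.05; 1:1 allocation; d entered 0.6666667.

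**Method.** Two-sample t-test with n per group: df = 2n − 2, noncentrality δ = d × √(n/2). Power is the probability that a noncentral t with these parameters falls outside ± the critical t.

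**Reproducing the plan.** At d = 0.6666667:
- n = 37: δ = 0.6666667 × √18.5 = 2.867, critical t = 1.993, power 80.8%. At 36 per group power is 79.7%, so 37 is the minimum for 80%.
- n = 50: δ = 0.6666667 × √25 = 3.333, critical t = 1.984, power 91.0%.

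Both agree with the printed output. The software ran correctly; the question is the input.

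**Where could 0.6667 come from?**
- Rounded difference: 1000 − 800 = 200 mL; 200/350 = 0.571.
- Unrounded difference: 0.40 × 2642 − 0.30 × 2642 = 1056.8 − 792.6 = 264.2 mL; 264.2/350 = 0.755.
- Control SD: 200/308 = 0.649; 264.2/308 = 0.858.
- Backwards from d: 200/0.6667 = 300 mL as SD, or 0.6667 × 350 = 233 mL as difference.

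No stated pair gives 0.6667, and neither 300 mL nor 233 mL appears in the document.

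**Consequences** (the last column is 50 minus the n for 80% power):

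| Difference / SD (mL) | d | n per group for 80% | Power at 37 | Power at 50 | Losses per group that 50 can absorb |
|---|---|---|---|---|---|
| As entered | 0.667 | 37 | 80.8% | 91.0% | 13 |
| 200 / 350 | 0.571 | 50 | 67.9% | 80.8% | 0 |
| 264.2 / 350 | 0.755 | 29 | 89.3% | 96.2% | 21 |
| 200 / 308 | 0.649 | 39 | 78.7% | 89.5% | 11 |

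No withdrawal rate is stated, so for 200/350 here is a range of completers per group: 49 gives 79.96%, 45 gives 76.5%, 40 gives 71.4% and 37 gives 67.9%.

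**The 20% figure.**
- Post-operative capacity, rounded losses: 2642 − 800 = 1842 against 2642 − 1000 = 1642 mL; 1842/1642 = 1.122, or 12.2% higher.
- Unrounded: 0.70 × 2642 = 1849.4 against 0.60 × 2642 = 1585.2 mL; 0.70/0.60 = 1.167, or 16.7% higher.
- Relative reduction in loss: 1 − 800/1000 = 20% rounded; 1 − 30/40 = 25% unrounded.

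So 20% fits only the relative reduction in the rounded loss, which is how section 6.0 uses it.

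**The case against.** The best defence is that 200 mL was plainly the sized difference. Section 11.0 carries the rounded losses forward, section 6.0's 20% fits only them, and 200/300 is exactly the entered d. An SD near the stated control value of 308 mL may then have been used, with 350 the stray figure. In that case power at 50 per group is 89.5% against the stated 91%, and the practical effect is small. This is a reasonable inference and it limits what can be claimed. It does not remove the fault: the plan states 350 as the shared SD, and 300 nowhere.

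A reader might infer that the trial is underpowered. The documents do not support that. Power at 50 per group is at least 80% in every case tabulated, and on the 264 mL basis it exceeds the stated 91%. Nor do they support a specific increase in enrolment: with no withdrawal rate given, any inflated number would rest on one back-calculated from 37 and 50 (13/50 = 26%).

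A reader might also infer from the one-sided alternative and the two primary hypotheses that the test is undefined or its error rate inflated. Neither follows. The analysis sentence and both power runs agree on a two-sided test of change, and testing a directional hypothesis two-sided is conservative. The inequality sign in the null may be a misread symbol. The line "The primary outcome of interest is the inspiratory capacity obtained in the PACU via the incentive spirometer" names the measured variable. Because subjects are randomised after the baseline breaths (section 10.0), the expected difference in mL between groups is the same for capacity and for change. Nor would a true 20% capacity gain be missed: it is 0.20 × 1585.2 = 317 mL, or 0.20 × 1642 = 328 mL, with at least 97% power at 37 per group and SD 350. On wording, then, only the 20% label and the form of the hypotheses need correction.

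**Conclusion.** The point holds as an error in the sample-size input. The entered d = 0.667 cannot be obtained from any difference and SD that the plan states, so 37 per group, 80% and 91% do not follow from its own assumptions.

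Taken literally (200 mL, SD 350), the requirement is 50 per group rather than 37, power with full retention is 80.8% rather than 91%, and the attrition allowance is nil. With 264 mL and SD 350, the plan understates its power (96.2% at 50). With 200 mL and SD 308, the stated figures are nearly right. The documents do not settle which was meant. The results assume a two-sample t-test on change, equal groups and a common SD.

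The hypothesis wording is secondary. The 20% capacity figure is not the sized effect, and the printed hypotheses do not match the two-sided test, but correcting either changes neither the test nor N.

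**What to change.** In section 11.0, the sponsor should choose one difference in mean loss (200 mL from the rounded figures, or 264 mL from 30% against 40% of 2642 mL) and one SD: 350 mL, or the SD actually used, stated and justified. From that pair, restate d, the n per group for 80% power, the power at 50 per group, and how many withdrawals per group 50 can absorb. Enrolment stays at 50 per group.

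As secondary wording:
- Replace the 20% capacity claim with the chosen difference in mean loss. Section 6.0's 20% stands on the 200 mL basis and becomes 25% on the 264 mL basis.
- Write the null as equal mean change in the two groups and the alternative as different mean change, to match the planned two-sided test.

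The cost is two reruns of a power calculation and a few lines of text, with no change to the test or the data collected. On the 200 mL and SD 350 basis, the sponsor would also have to acknowledge that 50 per group gives 80.8% power only if nobody is lost.

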## 10.0 Study Design / Methods

- After obtaining informed consent, the subjects will be provided with an incentive spirometer. They will be educated in its use and will then proceed to take three separate maximum exertion inspiratory capacity breaths. All three measurements will be recorded and the subjects will then be randomized to the control or intervention group.
- They will proceed to the operating room where the existing baseline ERAS protocol for colorectal or hepatobiliary surgery will be implemented during their surgery. In addition to the existing protocols, the five lung protective strategies listed above will also be implemented throughout the course of the surgery for the intervention group.
- In the PACU, the subjects will be asked at the 30 minute, 1 hour, and 2 hour marks (time zero will be arrival to PACU) to once more take three separate maximum exertion inspiratory capacity breaths and all three measurements will be recorded.
- If the subjects are unable or unwilling to comply, this will be documented as well and re-attempted at the next scheduled study documentation milestone.
- The information that will be pulled from the subject's medical record will include age, gender, weight, height, BMI, O2 saturation, average intra-op tidal volume, and the absence or presence of supplemental O2 use.
- The data collected for the intervention subjects who will have the standardized lung protective strategies applied will then be compared to the control subjects who underwent the same surgeries and had the same colorectal and hepatobiliary protocols implemented, but without the use of standardized lung protective strategies.

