**t tests - Means: Difference between two independent means (two groups)**

**Analysis:** A priori: Compute required sample size

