**Output:**

Noncentrality parameter $\delta$	= 2.8674419
Critical t	= 1.9934636
Df	= 72
Sample size group 1	= 37
Sample size group 2	= 37

Sample size was determined using G\*Power version 3.1.9.2 software. Using preliminary data, we estimate that we will need 37 subjects in each group (N=74) to have sufficient power (80%) at alpha=0.05 to test the hypothesis of a difference in mean change in IS for the two groups. To account for attrition due to withdrawals, we intend to enroll 50 patients per group. In the event that no withdrawals occur, enrolling 100 subjects (50 in each group) will give 91% power to distinguish between the two groups.

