**Input:**

Tail(s)	= Two
Effect size d	= 0.6666667

$\alpha$ err prob	= 0.05
Sample size group 1	= 50
Sample size group 2	= 50
Output: Noncentrality parameter $\delta$	= 3.3333335
Critical t	= 1.9844675
Df	= 98
Power (1- $\beta$ err prob)	= 0.9099634

Baseline clinical and demographic factors for each group will be collected. Categorical data will be compared across the two groups with Chi-square tests of homogeneity and continuous data will be compared with t-tests for means. Covariates determined to be associated with IS measurement will be assessed for inclusion in a multivariate linear model.

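### The primary test uses pre-randomisation IS only by subtraction; an ANCOVA on baseline IS would cost almost nothing and may be clearly more precise

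*Combined protocol and SAP*

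**What the plan says.** Section 10.0 has each subject take three maximal breaths on the incentive spirometer after consent: "All three measurements will be recorded and the subjects will then be randomized to the control or intervention group". Baseline IS is therefore a pre-randomisation covariate available for everyone.

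Section 11.0 then sets the primary analysis: "The primary analysis will be a two-sided test of mean change in IS after surgery compared to pre-surgery IS". The sample-size output in the same section is for "t tests - Means: Difference between two independent means (two groups", and the conclusion drawn from it is that 37 per group are needed "to have sufficient power (80%) at alpha=0.05 to test the hypothesis of a difference in mean change in IS for the two groups". No covariate appears in the primary test or in its sizing.

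The planning values, also in section 11.0, are:

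- Baseline: "we assume that the IS before surgery is 2642 mL (se=140; std=610".
- Control arm: "If the control group IS decreases by 40%, the mean change in the control group will be ~1000 mL (std dev=308".
- Intervention arm: "Assuming the intervention group IS decreases by 30%, the mean change in the intervention group will be ~800 mL. Assume shared std dev=350".

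The only adjusted analysis is at the end of section 11.0: "Covariates determined to be associated with IS measurement will be assessed for inclusion in a multivariate linear model". It is not called primary, it does not name baseline IS, and its covariates are to be chosen after looking at associations in the data.

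**The concern.** A change score is a baseline adjustment with the slope fixed at 1. It is fully efficient only when the loss of IS is unrelated to the starting value. If patients with larger baseline capacity lose more millilitres, the slope of post-operative on pre-operative IS is below 1. The change score then carries baseline variation that an ANCOVA would remove.

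The plan itself expresses the expected losses as percentages of baseline, at least for the group means, and that pattern points to a slope below 1. The trial is small and expects attrition, so it may be giving up precision that needs no extra patients and no extra data.

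**Working it through.** **Inputs (section 11.0).** Baseline IS 2642 mL, SD 610; SD of change 350; 50 per group enrolled, 37 per group required; two-sided alpha 0.05. Not in the documents: the post-operative SD and the pre-post correlation. These are covered by scenarios.

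**Reproducing the plan's figures.** The entered effect size of 0.667 equals 200/300. With the noncentral t distribution it gives 37 per group (noncentrality 2.867, critical t 1.9935, power 0.808) and power 0.910 at 50 per group. Both match the plan. The stated shared SD of 350 gives 200/350 = 0.571 instead. That mismatch is a separate matter; the main results below use the stated 350.

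**Unadjusted test, 50 per group.** SE = 350 × √(2/50) = 70.0 mL. Half-width = 1.984 × 70.0 = 138.9 mL, whatever the true difference. Power at 200 mL is 0.808.

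**ANCOVA.** Residual variance = 350² × (1 − R²), where R² is the squared within-arm correlation of change with baseline. One degree of freedom is lost (97 instead of 98). Estimating the slope inflates the variance by an expected factor of 1 + 1/(2n − 4), which is 1 + 1/96 at n = 50.

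(a) *Change unrelated to baseline.* R² = 0. Half-width is 138.9 mL, or 139.7 mL with the slope cost. Power at 200 mL is 0.8075, or 0.8035 with the slope cost. At 37 per group, power goes from 0.6790 to 0.6727 at worst.

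(b) *Equal pre- and post-operative SDs.*
- ρ = 1 − 350²/(2 × 610²) = 0.835
- R² = (1 − ρ)/2 = 0.082
- Residual SD = 335.3; SE = 67.1; half-width = 133.1 mL
- Equivalent unadjusted n = 50/(1 − 0.0823) = 54.5 per group

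(c) *Each patient's loss proportional to baseline, 40% in control and 30% in intervention, SD of change 350 in each arm, one common slope of 0.35.*
- Residual variance = 350² − [(0.16 + 0.09)/2 − 0.05²] × 610² = 122,500 − 0.1225 × 372,100 = 76,918
- R² = 0.372; residual SD = 277.3; SE = 55.5; half-width = 110.1 mL
- Equivalent unadjusted n = 50/(1 − 0.372) = 79.6 per group

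The losses in (c) imply a difference of 0.10 × 2642 = 264 mL, so 264 mL is the consistent comparison for that scenario; 200 mL is the plan's rounded figure.

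| SD of change 350 | Half-width, n = 50 | Power at 200 mL, n = 50 | Power at 264 mL, n = 50 | Power at 264 mL, n = 37 |
|---|---|---|---|---|
| Unadjusted | 138.9 mL | 80.8% | 96.2% | 89.3% |
| ANCOVA (b) | 133.1 mL | 84.0% | 97.4% | 91.7% |
| ANCOVA (c) | 110.1 mL | 94.6% | 99.7% | 98.1% |

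Rows (b) and (c) omit the slope cost. Including it adds 0.6 to 0.7 mL to the half-widths and takes at most 0.4 points off these power figures.

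With the plan's entered effect size (SD 300, 200 mL, 50 per group), power is 91.0% unadjusted, 90.7% to 91.0% in (a) and 92.6% in (b).

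**Simulation check of (c), 20,000 trials.** At 50 per group and 264 mL, rejection was 0.963 unadjusted and 0.997 with ANCOVA, with mean SEs of 69.8 and 55.6 mL. With no effect (35% loss in both arms) it was 0.048 and 0.047, so both methods hold the 5% level.

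Scenario (c) is not an upper limit. A post-operative SD of 457.5 mL (75% of 610) with the same SD of change gives a variance ratio of 0.554, a reduction of about 45%.

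**The case against.** The planned analysis is a recognised one, and the trial is sized for exactly that test, so there is no inconsistency here to correct. The gain cannot be known from the documents. The largest figure rests on an individual-level proportional model, whereas section 11.0 uses 40% and 30% only to derive group means. On the consistent 264 mL comparison at full enrolment, the unadjusted test already has 96.2% power. The linear model at the end of section 11.0 might well come to include baseline IS.

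Much of this is fair and limits the claim: the gain may be nil, and (c) is an assumption. It does not remove the point, because the possible loss is bounded at a fraction of a percentage point of power while the possible gain is not small. A covariate model that leaves baseline IS unnamed and is not primary does not commit the trial to the adjustment.

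Two further objections stand as caveats. First, sections 4.0 and 14.0 end participation after randomisation for several reasons, including inability to adhere to the lung protective interventions. If those subjects are left out of the analysis, the protection of randomisation is weakened for the planned test and for ANCOVA alike. Second, the post-operative measure is not fixed. Section 10.0 records three breaths at each of 30 minutes, 1 hour and 2 hours; section 4.0 points to the third breath at 2 hours and section 1.0 to a PACU mean. Either analysis needs that settled.

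**Conclusion.** The point holds as one of efficiency. The unadjusted test of change is valid under randomisation, but it may give up precision that the trial has already paid for. The size depends on how loss relates to baseline, which the documents do not say:

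- no gain if they are unrelated;
- about 8% less variance (worth about 4 patients per group) if pre- and post-operative SDs are equal;
- about 37% less variance (worth about 30 patients per group) if individual losses are proportional to baseline at the plan's percentages.

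The worst-case cost is about 0.4 points of power at 50 per group and 0.6 at 37. All of this takes the plan's SDs of 610 and 350 mL as given. The change should be made, but the trial is not invalid without it.

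**What to change.** In section 11.0, make the primary analysis an ANCOVA of post-operative IS on arm and baseline IS, with a two-sided alpha of 0.05. Define baseline IS as the mean of the three pre-operative breaths. Using change in IS as the outcome gives the same arm effect once baseline is in the model, so the hypothesis can still be worded in terms of change. Use the same post-operative measure as the change score would use, and name it explicitly. Report the adjusted difference with its 95% confidence interval, and keep the unadjusted two-sample test of change as a sensitivity analysis.

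The cost is wording only. Baseline IS is already collected before randomisation under section 10.0, and no extra subjects, visits or measurements are needed. The sample size need not change: the existing calculation stays essentially correct as a conservative figure for the adjusted analysis, apart from the small worst-case loss above.

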## 4.0 Study Endpoints (if applicable)

- The end-point of the study will be completion of the 3rd incentive spirometry breath measurement at the 2 hour mark, whether it be in PACU or on the inpatient floor
- Study termination would include need for post-operative mechanical ventilation, need for post-op BIPAP/CPAP, admission to ICU, or inability to adhere to lung protective interventions due to subject intolerance.

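### The primary test has no stated post-operative time or breath summary, and the 20% higher mean capacity named as a primary hypothesis does not follow from the plan's own figures

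*Combined protocol and SAP*

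**What the plan says.** **Test.** Section 11.0 (Data Management): "The primary analysis will be a two-sided test of mean change in IS after surgery compared to pre-surgery IS". The sample size output that follows is for a difference between two independent means, which uses one value per patient.

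**Data.** Section 10.0 records three maximal breaths before surgery. After surgery: "In the PACU, the subjects will be asked at the 30 minute, 1 hour, and 2 hour marks", again with three breaths each time. A missed reading is handled operationally: "If the subjects are unable or unwilling to comply, this will be documented as well and re-attempted at the next scheduled study documentation milestone".

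**Outcome.** Section 11.0: "The primary outcome of interest is the inspiratory capacity obtained in the PACU via the incentive spirometer". Section 4.0 places the study's end-point at the third "incentive spirometry breath measurement at the 2 hour mark, whether it be in PACU or on the inpatient floor". Sections 1.0 and 2.0 refer to a mean capacity without saying whether the mean is over breaths, times or patients.

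**Hypotheses.** Section 11.0 introduces a primary hypothesis twice. In the first, intervention patients "will have 20% superior mean inspiratory capacity breaths via incentive spirometry compared to the non-intervention controls". The second reads: "Our primary hypothesis is that use of lung protection protocol will result in smaller change in lung function". Section 6.0 uses 20% in another sense, as a difference between the arms in the size of the decrease.

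**Planning figures (section 11.0).** Baseline 2642 mL (SD 610); control decrease 40%, about 1000 mL; intervention decrease 30%, about 800 mL; "Assume shared std dev=350".

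**Covariates.** Section 11.0 ends by leaving covariates to be considered for a linear model. It does not commit to adjusting for baseline.

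**The concern.** Each patient supplies three baseline and nine post-operative readings, and the plan does not say how they become the one number that is tested. The available pointers disagree. Section 4.0 suggests a single third breath at 2 hours and allows it to be taken on the floor. Section 11.0 confines the outcome to the PACU. Sections 1.0 and 2.0 suggest some kind of mean. Two careful analysts could follow the document and report different primary results, and nothing rules out settling the choice once the data are known.

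The two hypotheses add a second uncertainty. One is about the level of capacity and the other about the change. A reader cannot tell which defines the primary outcome, or what difference the trial was designed to find.

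**Working it through.** **1. The plan's own sample size.** Noncentral t, two-sided alpha 0.05, with the entered effect size d = 0.6667. At 37 per group, δ = 0.6667 × √(37/2) = 2.867, critical t = 1.993 and power is 80.8%. At 50 per group, δ = 3.333 and power is 91.0%. Both match the printed output, which confirms a single-value, two-sample test of change.

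**2. From readings to one value.** Post-operative: 3 times × 3 breaths = 9. Baseline: 3.

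| Place | Time | Breath summary | Location |
|---|---|---|---|
| 11.0, primary test | after surgery, unspecified | none | none |
| 11.0, primary outcome | none | none | PACU |
| 4.0, end-point | 2 h | third breath | PACU or floor |
| 1.0 | none | a mean, of what is not said | PACU |
| 2.0 | none | a mean, of what is not said | none |
| 10.0, procedures | 30 min, 1 h, 2 h | all three recorded | PACU |

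No row supplies a time and a breath summary that are also tied to the test.

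**3. Does the planning case give a 20% higher level?**
- Unrounded: control 0.6 × 2642 = 1585 mL; intervention 0.7 × 2642 = 1849 mL. Difference 264 mL; ratio 1.167, so 16.7% higher.
- Rounded: 2642 − 1000 = 1642 mL; 2642 − 800 = 1842 mL. Difference 200 mL; ratio 1.122, so 12.2% higher.
- A level 20% higher: 1.2 × 1585 = 1902 mL. This needs a difference of 317 mL, which is an intervention-arm decrease of (2642 − 1902)/2642 = 28%.

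**4. Section 6.0's 20% difference in the decrease.** Rounded: 200/1000 = 20%, which agrees. Unrounded: 264/1057 = 25%, which does not.

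**5. Level versus change.** Randomisation follows the baseline breaths, so both arms share an expected baseline μ₀. Then (μ_I − μ₀) − (μ_C − μ₀) = μ_I − μ_C. The expected arm difference in mL is the same on either scale; only the precision differs.

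**6. Type I error if the time were chosen after seeing data.** Three equally correlated test statistics, each compared with ±1.96, with the smallest p-value reported. By simulation, 12.5% at correlation 0.5, 10.9% at 0.7 and 8.4% at 0.9. The correlations are assumed; the documents give none.

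**7. Gain from adjusting for baseline.** Take baseline SD 610, change SD 350 and post-operative SD s (assumed). Since s² = 610² + 350² + 2r(610)(350), the correlation of baseline with change is r = (s² − 610² − 350²)/(2 × 610 × 350). The residual SD is 350√(1 − r²). Power is for 200 mL at 50 per group.

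| Analysis | r | Residual SD | Power |
|---|---|---|---|
| Unadjusted change | – | 350 | 81% |
| Adjusted, s = 610 | −0.29 | 335 | 84% |
| Adjusted, s = 366 (0.6 × 610) | −0.84 | 187 | above 99% |

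A smaller s makes r more negative, so 84% is the floor for any s up to 610.

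**The case against.** The strongest reply is that the plan names one primary analysis, a test of change, and sizes only that. No test of level is planned. As step 5 shows, level and change estimate the same treatment effect in mL. This stands. A reader might infer that the trial has two competing primary effects, or that 20% is a bar for success. The documents support neither: the 20% appears only in a hypothesis and in the sample size rationale, and section 6.0's version agrees with the rounded changes.

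A second reply is that section 4.0 already fixes the third breath at 2 hours. That falls short. The sentence marks completion of the study, is followed by conditions for termination, and is not connected to the test. Taken as the definition, it would conflict with the PACU-only outcome whenever the reading is taken on the floor.

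A third reply is that the 8–13% error rate describes conduct, not the plan. This also stands. A reader might infer that a time will be picked for its result, but no section suggests it. The figure is the cost of leaving the choice open.

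Finally, a change score already uses baseline, so adjustment may look like a matter of taste. But baseline IS is collected anyway, and step 7 shows a gain at every post-operative SD up to 610 mL.

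**Conclusion.** The point holds in this form. The primary variable is not uniquely defined: nine post-operative and three baseline readings are collected, and no time or breath summary is attached to a test that needs one value per patient. The PACU-only outcome and the PACU-or-floor end-point also disagree. The hypothesis of a 20% higher mean is contradicted by the plan's own figures (16.7% or 12.2%; 20% would need 317 mL), and the 40%/30% and 1000/800 mL figures give different relative reductions (25% and 20%).

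The harm is an undefined primary variable and an inconsistent target. It is not a demonstrated inflation of type I error: the 8–13% applies only if the time is chosen after seeing data, with assumed correlations of 0.9–0.5. Nor does the point show a loss of power. The gain from adjustment (81% to at least 84%) assumes a 200 mL difference, a change SD of 350 and a post-operative SD of at most 610. That the entered effect size of 0.667 is not 200/350 is a separate matter and carries no weight here.

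This should be corrected before data are seen. It does not prevent the trial from running.

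**What to change.** Before data are seen:

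1. Name one primary time and one breath summary, apply the same summary at baseline, and use that definition in every section. One example is the mean of the three breaths at 2 hours, in PACU or on the floor, with 30 minutes and 1 hour secondary. Any single named choice cures the ambiguity. Align the PACU and floor wording with it.
2. Delete the hypothesis of a 20% higher mean or restate it as a difference in change. Make the percentage and mL figures agree. Section 6.0 can stay if the rounded changes are kept.
3. Make the primary analysis a linear model for the arm difference adjusted for baseline IS, in place of the unadjusted change-score t-test.
4. State how missed readings enter the analysis. Re-attempting at the next mark does not help at 2 hours, because no mark follows. Optionally, estimate the 2-hour difference from a baseline-adjusted repeated-measures model on all three times, so that patients who miss 2 hours still contribute.

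**Cost.** Items 1 and 2 are wording. Item 3 uses data already collected and costs one degree of freedom. The optional model in item 4 adds a missing-at-random assumption, which needs a sensitivity analysis. It does not cover patients with no post-operative reading, including those withdrawn under section 14.0 before any reading, who need a separate rule. No new visits, measurements or patients are required.

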## 6.0 Number of Subjects

- This study will include 100 subjects in order to detect a 20% difference in the anticipated decrease in incentive spirometry inspiratory capacity breaths for the control and intervention groups.

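### The effect size used for the sample size (d = 0.667) does not follow from the stated 200 mL difference and SD of 350 (d = 0.571); on those inputs power is 68% at 37 per group, not 80%, and 81% at 50, not 91%

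*Combined protocol and SAP*

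**What the plan says.** Section 11.0 Data Management sets out the assumptions in millilitres. Baseline inspiratory capacity is 2642 mL. With a 40% fall in controls, "the mean change in the control group will be ~1000 mL (std dev=308"). For the other arm and the common SD it says: "Assuming the intervention group IS decreases by 30%, the mean change in the intervention group will be ~800 mL. Assume shared std dev=350".

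The G*Power input that follows is a two-tailed, two-group t test with alpha 0.05, power 0.8, equal allocation and d = 0.6666667. The output is 37 per group, and the text concludes that "we will need 37 subjects in each group (N=74) to have sufficient power (80%) at alpha=0.05". Enrolment is then raised to 50 per group to allow for withdrawals. A second G*Power run, again with d = 0.6666667, supports the statement that, with no withdrawals, "enrolling 100 subjects (50 in each group) will give 91% power to distinguish between the two groups".

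Section 6.0 gives the target in relative terms: "This study will include 100 subjects in order to detect a 20% difference in the anticipated decrease".

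**The concern.** The standardised effect is the difference in means divided by the common SD. The text gives both quantities, and their ratio is 0.571, not 0.667. Since the required sample size varies with 1/d², a discrepancy of this size matters.

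This calculation is the only justification for enrolling 100 subjects. If its main input does not match the assumptions printed just before it, a reader cannot tell which effect and SD the trial rests on, and the stated powers of 80% and 91% are not properties of the design as described.

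The withdrawal allowance is also at stake. The plan treats 37 per group as the requirement and the remaining 13 as a margin. Withdrawals are built into the design: Section 14.0 removes subjects who need postoperative ventilation, BIPAP or CPAP, or immediate ICU admission, or who do not meet the ventilation goals, and Section 4.0 lists similar events. If the true requirement is 50, that margin does not exist.

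**Working it through.** **Inputs, all from Section 11.0.** Mean changes of about 1000 and 800 mL; shared SD 350 mL; control-group SD 308 mL; baseline 2642 mL with falls of 40% and 30%; two-sided alpha 0.05; target power 80%; equal allocation; d entered as 0.6666667.

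**Method.** Two-sample t test with n per group: df = 2n − 2, noncentrality δ = d·√(n/2), and power = P(|T| > critical t), where T is noncentral t with parameter δ. G*Power uses the same method.

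**Step 1: reproduce the plan's figures from d = 0.6667.**
- n = 37: δ = 0.6667 × √18.5 = 2.867, critical t = 1.993, power 80.8%. At n = 36 power is 79.7%, so 37 is the smallest n that reaches 80%.
- n = 50: δ = 0.6667 × √25 = 3.333, critical t = 1.984, power 91.0%.

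These match the printed output. The software was run correctly on the value entered.

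**Step 2: look for d = 0.6667 among the stated inputs.** The unrounded falls are 0.40 × 2642 = 1056.8 mL and 0.30 × 2642 = 792.6 mL, a difference of 264.2 mL.

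| Difference (mL) | SD (mL) | d | n per group for 80% | Power at 37 | Power at 50 |
|---|---|---|---|---|---|
| 200 | 350 (shared SD, as stated) | 0.571 | 50 | 67.9% | 80.8% |
| 200 | 308 (control SD) | 0.649 | 39 | 78.7% | 89.5% |
| 200 | √((308² + 350²)/2) | 0.607 | 44 | 73.1% | 85.2% |
| 264.2 | 350 | 0.755 | 29 | 89.3% | 96.2% |
| 264.2 | 308 | 0.858 | 23 | 95.4% | 98.9% |

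None gives 0.6667. With a 200 mL difference, the SD would have to be 200/0.6667 = 300 mL. With SD 350, the difference would have to be 0.6667 × 350 = 233 mL. Neither value is stated. A one-sided test on 200/350 would need 39 per group, but the plan specifies two sides, and sidedness does not alter d.

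**Step 3: redo the calculation from 200 mL and SD 350.** d = 200/350 = 0.5714.
- n = 37: δ = 0.5714 × √18.5 = 2.458, power 67.9%.
- n = 50: δ = 0.5714 × √25 = 2.857, power 80.8%.
- Smallest n for 80%: 50 per group (49 gives 79.96%).
- Smallest n for 91%: 68 per group.

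**Step 4: effect of withdrawals.** Going from 50 to 37 per group is a loss of 13/50 = 26%. With 45, 40 or 37 evaluable per group, power is 76%, 71% or 68%. At 37, the probability of missing the assumed effect is about 32%, against the 20% the plan accepts.

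**The case against.** The arithmetic is not in dispute. The objections concern how it is read.

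**The printed SD may be the slip.** d = 0.6667 is exactly 200/300, and the control SD of 308 is close to 300. If SD 300 was intended and 350 was printed by mistake, then 37 per group and 91% are right and only the narrative is wrong. This cannot be excluded, but nothing in the documents supports it. The plan names 350 as the shared value after giving 308 for controls, and 308 itself does not produce 0.6667.

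**The means are approximate.** On the unrounded percentages the difference is 264 mL, and with SD 350 the design has more power than claimed: 89% at 37 and 96% at 50. The direction of the error therefore depends on which difference was meant. This limits how firmly a shortfall can be asserted, but it does not rescue the calculation, because 0.755 is not 0.667 either. Section 6.0 also favours 200 mL: a 20% difference in the decrease fits 200/1000, whereas 264.2/1056.8 is 25%.

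**The consequence is modest.** Even with 200 mL and SD 350, 100 completers reach the 80% target. That is true, but it requires no withdrawals, and the plan itself expects some.

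What stands is that the shortfall is conditional on the 200 mL difference and SD of 350 as printed. The inconsistency itself is not conditional on anything.

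**Conclusion.** The concern holds. The d entered in both G*Power runs cannot be obtained from any pair of assumptions the plan states. Taking the plan at its word (200 mL, shared SD 350, two-sided alpha 0.05, equal groups), power is 12 percentage points below the stated figure at 37 per group (68% against 80%) and 10 points below at 50 (81% against 91%). The requirement for 80% power is 50 evaluable per group, so planned enrolment leaves no allowance for withdrawals.

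This rests on the rounded means as printed. With SD 350, the plan's figures give 81% or 96% power at 50 per group, depending on whether the difference is 200 or 264 mL, and 91% on neither. The sample-size justification is wrong as written and must be corrected.

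**What to change.** First establish which difference and SD were intended, and state the difference, the SD and d together so that the third follows from the other two. Then rerun both calculations.

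If 200 mL and SD 350 stand, enter d = 0.571, remove the 37-per-group requirement and the 91% figure, and use wording such as: *With a 200 mL difference in mean change and a common SD of 350 mL (d = 0.571), 50 evaluable subjects per group give 81% power at two-sided alpha 0.05; if withdrawals leave 37 per group, power is 68%.* The sentence presenting 50 per group as 37 plus an attrition margin must go as well.

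If SD 300 or the 264 mL difference was meant, correct the stated assumption, say what supports it, and recompute from there.

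The cost is protocol and SAP wording only. Enrolment can stay at 100, provided the plan acknowledges that on the first route withdrawals take power below 80%. On that route the stated power becomes less favourable; no extra patients are needed.
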